##### 6.12.8.3 Hepatotoxicity

If plasma AST and/or ALT concentrations  $> 3 \times$  ULN are detected, the investigator will record in the source documents:

- the date corresponding to the date of the laboratory abnormality
- the type, frequency, and dose of any concurrent medications or supplements taken by the subject within the 14 days of the detected abnormality
- any symptoms or change in physical exam that have occurred since the prior assessment

The investigator should perform additional laboratory and imaging tests to attempt to establish the cause of the AST and ALT elevations, including ruling out any potential contribution from bone or muscle etiologies.

Any clinically significant increase in hepatic enzymes and specifically any ALT or AST > 3 x ULN requires immediate repeat test within 48 to 72 hours to confirm the hepatic enzyme elevation. Testing should be repeated based on the clinical situation at least every 96 hours (4 days) until ALT and AST return to < 2.5 x ULN or until the liver function test results are stable and significant changes are not expected anymore. Study medication should be stopped and the event should be reported as a laboratory AE within the CRF if the enzyme elevation is confirmed or worsening.

Should it be determined that the etiology is an unrelated acute or chronic medical condition (e.g.; NASH, Hepatitis A) and the return of LFT abnormalities to normal is unlikely during the course of the illness, further testing and follow up is at the investigator's discretion.

Hepatotoxicity will be diagnosed and entered as an AE should any of the following occur:

- ALT or AST > 8 x ULN
- ALT or AST > 3 x ULN and total bilirubin > 2 x ULN or INR > 1.5
- ALT or AST > 3 x ULN with the appearance of fatigue, nausea, vomiting, right upper quadrant pain or tenderness, fever, rash, and/or eosinophilia (> 5%)

In the event of hepatotoxicity, investigational product should be permanently discontinued. The investigator is encouraged to consult with the Medical Monitor regarding diagnostic evaluation for the hepatic enzyme elevations. Consultation with a hepatologist may also be appropriate in some circumstances.

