#### 6.12.8.6 Acute Kidney Injury

Evaluation and management of subjects with and at risk for acute kidney injury (AKI) should be performed during the study period based on the Kidney Disease: Improving Global Outcomes (KDIGO) Clinical Practice Guideline in 2012 ([KDIGO Clinical Practice Guideline for AKI, 2012](#)). The classification/staging System for AKI is described in [Appendix 5](#).

[figure not shown]
If serum creatinine increases suggesting a possible stage 1 AKI, the investigator should confirm the increase in serum creatinine within one week of learning the result and enter an

AE into the CRF if the serum creatinine does not spontaneously returns to  $< 0.3$  mg/dL from baseline. The investigator should encourage the subjects to maintain hydration and pursue any additional clinically relevant investigations to elucidate the cause or potential consequences of the decline in renal function. Study drug administration may be suspended if clinically indicated until the creatinine value returns to  $< 0.3$  mg/dL from baseline. Serum creatinine should be monitored based on the investigator's judgment until creatinine returns to baseline level, within 0.3 mg/dL difference.

If serum creatinine increases or other signs suggesting a possible stage 2 or 3 AKI, the subject should be monitored daily and nephrology consultation or hospitalization within 24 h should be considered. Study drug administration should be stopped until the creatinine value returns to  $< 0.3$  mg/dL from baseline. If potentially life-threatening conditions (*i.e.*, uremia, pulmonary edema, arrhythmia, disseminated intravascular coagulation, hyperkalemia, metabolic acidosis) are present occurring in the setting of a possible stage 2 or 3 AKI event, the administration of study drug must be stopped and the medical monitor should be informed. The medical monitor will advise on whether the study drug can be restarted after the resolution of the potentially life-threatening condition. Local laboratory testing will be acceptable when immediate lab results are necessary for clinical assessment.

If interrupted, study drug may be reinitiated when serum creatinine returns to within 0.3 mg/dL of the randomization value or if renal function remains 0.5 mg/dL above the randomization value but an alternative cause of the worsened renal function has been identified. Dosing of study drug will be permanently discontinued if the subject is to start dialysis or other renal replacement therapies.

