**Table 3. Classification/Staging System for Acute Kidney Injury**

Stage	Serum creatinine criteria	Urine output criteria
1	1.5 to 1.9 times baseline or ≥ 0.3 mg/dL (≥ 26.5 μmol/L) increase from baseline	<0.5 mL/kg/h for 6 to 12 h
2	2.0 to 2.9 times baseline	< 0.5 mL/kg/h for ≥ 12 h
3	3.0 times baseline, or Increase in serum creatinine to ≥4.0 mg/dL (≥ 353.6 μmol/L), or Initiation of renal replacement therapy, or In patients < 18 years, decrease in eGFR to < 35 mL/min per 1.73 m 	< 0.3 mL/kg/h for ≥ 24 h or anuria for ≥ 12 h

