6. GENERAL ASPECTS FOR STATISTICAL ANALYSIS

6.1. GENERAL METHODS

Statistical methodology and analyses are in accordance with the principles outlined by the ICH E9 guidelines. All statistical analyses will be conducted using SAS statistical software version 9.3 or higher.

Tables, listings and figures (TLFs) will be produced in accordance with the principles outlined by the ICH E3 guidelines. For most summary statistics, data will be analyzed by the following treatment groups: Bexagliflozin 20 mg; Placebo. For 603B, unless otherwise specified, data will be analyzed by treatment in the 603B withdrawal period. Treatment in 603B withdrawal period will be further split by treatment sequence (as shown in Table 2). For integrated analyses, unless otherwise specified, summaries will be by total of all patients in the analysis set.

Data summaries will use descriptive statistics (number of subjects [n], mean, standard deviation [SD], Q1, median, Q3, minimum and maximum) for continuous variables, and frequency and percentage of subjects for categorical and ordinal variables, unless otherwise specified.

Unless otherwise specified, all statistical tests will be two-tailed using a 0.05 level of significance. All confidence intervals (CIs) will be two-sided 95% CIs.

Only scheduled visits will be included in by visit summaries. All visit assessment data will be included in shift tables and will appear in the subject listings.

No data imputation will be applied for missing values in safety analysis. Efficacy data imputation method will be described in Section 8.

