9.4. LABORATORY EVALUATIONS

Laboratory tests will include hematology panel, chemistry panel, serum lipids, and urinalysis testing. Hematology, HbA1c, chemistry, serum lipids, and urinalysis will be performed at the following time points: at the screening visit (Week - 12), on Day -1 visit, and at cumulative week 12, 24, and 36. A list of laboratory tests is included in Table 3.

Low density lipoprotein cholesterol (LDL-C) will be calculated by the Friedewald equation. If triglycerides are > 400 mg/dL, the calculated LDL-C value is invalid by this equation and will be set as missing. Direct LDL-C will be determined in subjects whose triglycerides are > 350 mg/dL at screening visit. All subsequent LDL-C of these subjects will be determined by the same direct LDL-C measurements only. If triglycerides are >350 mg/dL, a reflex test will be performed based on direct LDL measurement. The following algorithm will be used to obtain LDL-C values for the analyses:

1. Select subjects (based on the SI unit) who had screening triglycerides >3.4 or >350 based on the conventional unit
2. Take the LDL - direct measurement values only, throughout the study visits for those subjects
3. If screening triglycerides > 350 and no direct LDL-C values have been determined, take the calculated.

Among those subjects who have screening triglycerides >350 and have both calculated and direct LDL values, only the direct LDL will be analyzed.

Urinalysis microscopy will be conducted if the subject has a positive result on the leukocyte esterase or nitrite dipstick tests to clarify the significance of the finding. Results of glucose measurement in the urinalysis must be suppressed from the laboratory reports so the sponsor, investigators, study coordinators, pharmacists, study subjects, and the CEC members will remain blinded to the dosing assignment.

All scheduled and unscheduled results will be considered in tables that assess maximum severity.

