Observed values (in SI units) and change from baseline over time will be summarized for each scheduled visit and the end of the study visit. Laboratory data will be classified as low, normal, or high relative to the parameter's reference range. Laboratory abnormalities for each treatment will also be summarized with shift tables for selected parameters. All summary tables will be presented by treatment group and for each visit for study 603A and 603B. In addition, summaries based on assessments from both studies (603A and 603B) will also be presented by weeks of exposure of bexagliflozin (12 weeks, 24 weeks, and 36 weeks).

All continuous variables will be summarized by number of subjects [n], mean, SD, Q1, median, Q3, minimum and maximum and categorical variables will be summarized by frequency and percentage. For hematology, chemistry, and serum lipids, columns will be included for normal ranges and individual abnormal laboratory values will be flagged and clinical significance will be indicated. A listing for the microscopic examination will be provided for subjects who have a positive result from the urinalysis dipstick evaluation.

Table 3 List of Laboratory Tests

Hematology:
 
 • Hematocrit (Hct) • Hemoglobin (Hgb) • Mean corpuscular hemoglobin (MCH) • Mean corpuscular hemoglobin concentration (MCHC) • Mean corpuscular volume (MCV) • Platelet count • Red blood cell (RBC) count • White blood cell (WBC) count with differential 
Urinalysis:
 
 • Appearance • Bilirubin • Color • Glucose • Ketones • Microscopic examination of sediment • Nitrite • pH • Protein • Specific gravity • Urobilinogen 
Pregnancy test: Urine human chorionic gonadotropin (hCG) (only for females who are not diagnosed as postmenopausal)
	
Serum Chemistry:
 
 • Albumin (ALB) • Alkaline phosphatase (ALK-P) • Alanine aminotransferase (ALT) • Aspartate aminotransferase (AST) • creatinine kinase (CK) • Blood urea nitrogen (BUN) • Calcium (Ca) • Bicarbonate (HCO₃) • Chloride (Cl) • Creatinine • Glucose • Magnesium (Mg) • Phosphorus • Potassium (K) • Sodium (Na) • Total bilirubin • Direct bilirubin • Total cholesterol • HDL-cholesterol • LDL-cholesterol • Total protein • Triglycerides • Uric acid 
Glycemic control
 
 • HbA1c 
Population PK Sampling
 
 • Bexagliflozin plasma level
--	--

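### SAP 9.4 specifies no count by arm, from laboratory values, of subjects meeting the protocol's acute-kidney-injury creatinine criteria or ALT/AST multiples, and low/normal/high shifts cannot grade these harms

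*SAP*

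**What the plan says.** Protocol Appendix 6 (Table 3) defines stage 1 kidney injury by creatinine relative to baseline, "1.5 to 1.9 times baseline or ≥ 0.3 mg/dL", with higher multiples, or an absolute level of 4.0 mg/dL, for stages 2 and 3. Protocol 6.12.8.3 lists three hepatotoxicity criteria: "ALT or AST > 8 x ULN"; more than 3 times ULN with raised bilirubin or INR; and more than 3 times ULN with symptoms.

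SAP 9.4 handles laboratory data in four ways:
- Distribution summaries: "All continuous variables will be summarized by number of subjects [n], mean, SD, Q1, median, Q3, minimum and maximum", for values and changes by treatment and visit.
- Three categories: "Laboratory data will be classified as low, normal, or high relative to the parameter's reference range".
- Shift tables: "Laboratory abnormalities for each treatment will also be summarized with shift tables for selected parameters". The selected parameters are not named.
- One further sentence: "All scheduled and unscheduled results will be considered in tables that assess maximum severity". The SAP defines no laboratory severity grade.

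Individual abnormal values are flagged, and under SAP 6.1 "All visit assessment data will be included in shift tables and will appear in the subject listings". Protocol 9.7.2 plans the same kind of summary. eGFR, a stratification factor in 603A, is not in the SAP's Table 3 of laboratory tests.

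**The concern.** A stated safety objective (SAP 3.4) is to evaluate potentially adverse laboratory changes, and hepatotoxicity and renal failure events are of special interest (Protocol 6.12.8, SAP 9.3.3). The protocol gives numeric cut-offs for both harms, yet the laboratory analysis uses a scale on which those cut-offs do not appear. Followed as written, the laboratory tables would not show how many subjects per arm had a creatinine rise of stage 1 or more, or enzymes above 3 or 8 times ULN. For rises that reverse before confirmation, no other planned table would show it either. The randomised comparison of renal and hepatic laboratory harm would then rest on what investigators entered as adverse events and how those entries were coded.

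**Working it through.** **1. Units.** The documents give stage 3 as 4.0 mg/dL or 353.6 µmol/L, so 353.6 / 4.0 = 88.4 µmol/L per mg/dL. Then 0.3 × 88.4 = 26.52, against the stated 26.5. The threshold carries over correctly to the SI units that SAP 9.4 uses.

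**2. When a creatinine rise shows as a shift.** A rise r moves a subject from normal to high only if baseline lies between ULN − r and ULN. With baseline normally distributed (mean m, standard deviation s), the share that does not shift is

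1 − [Φ((ULN − m)/s) − Φ((ULN − r − m)/s)].

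The documents give neither the creatinine reference range nor the baseline distribution. Assumed: m = 0.8 to 1.0 mg/dL, s = 0.15 to 0.25, ULN = 1.0 to 1.4.

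One middle case: m = 0.9, s = 0.20, ULN = 1.2, r = 0.3. Φ(1.5) = 0.933 and Φ(0) = 0.500, so 0.433 shift and 57% do not (50% normal to normal, 7% high to high).

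The extremes for r = 0.3:
- m = 0.85, s = 0.15, ULN = 1.0: Φ(1) − Φ(−1) = 0.683, so 32% are hidden.
- m = 0.80, s = 0.15, ULN = 1.4: Φ(4) − Φ(2) = 0.023, so 98% are hidden.

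**3. Larger rises.** Simulated as 0.3 mg/dL plus an exponential excess, keeping only rises that stay below 2.0 times baseline. Medians and the last column come from 45 scenarios (means 0.8, 0.9, 1.0; three SDs; five ULNs). The 32% in the first row comes from a grid that also includes means 0.85 and 0.95.

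| Rise | Hidden from shift table | Median scenario | Scenarios above 50% |
|---|---|---|---|
| exactly 0.3 | 32% to 98% | 57% | 78% |
| 0.3 + mean excess 0.1 | 22% to 88% | 48% | 47% |
| 0.3 + mean excess 0.2 | 18% to 76% | 40% | 27% |

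With a mean excess of 0.3 the range is 17% to 69%.

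**4. Liver enzymes.** No distribution is needed. Any value above 3 times ULN is classed high, so it appears as a shift if baseline was normal, but in the same cell as 1.1 times ULN. Entry excludes ALT or AST only above 2.5 times ULN (Protocol 4.3). A subject entering at 2 times ULN who reaches 10 times ULN is therefore high to high.

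**5. The adverse-event route.**
- Hepatotoxicity criteria: entry as an adverse event is required (Protocol 6.12.8.3).
- Enzymes above 3 times ULN: a laboratory adverse event if confirmed or worsening (same section).
- Possible stage 1 creatinine rise: the investigator enters an "AE into the CRF if the serum creatinine does not spontaneously returns" to within the stated margin of baseline (Protocol 6.12.8.6). Rises that reverse are not entered.
- Special-interest events are then picked by preferred term from the adverse-event log (SAP 9.3.3), not by value.

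**6. Baseline in 603B.** SAP 6.2.1 takes the last value before double-blind dosing in 603B, which comes after 12 or 24 weeks on bexagliflozin. A creatinine rise already present by then is part of that baseline. The integrated summaries use the last value before first bexagliflozin.

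**7. What a direct count gives.** With 680 / 2 = 340 per arm, zero events would give a one-sided 95% upper bound of 1 − 0.05^(1/340) = 0.88%.

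**The case against.** The strongest reply is that these harms are already captured. Hepatotoxicity criteria must be entered as adverse events, and special-interest events are counted by number, percentage and rate per 100 patient-years for each treatment group (SAP 9.3.3.1). So a reader who infers that the thresholds are never counted goes too far, above all for the liver. What remains is dependence on investigator entry and coding, preferred-term tables that do not separate the enzyme multiples, and the loss of reversed stage 1 rises. SAP 12 also says that some tables will be prepared only for the integrated safety set because events are few. That set holds only bexagliflozin-exposed subjects (SAP 5.1.3), so rare events may lose their placebo column; the SAP does not say which tables these are.

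Second, leaving out transient rises is the protocol's own case rule. That is fair for adverse events, but it does not prevent a descriptive laboratory count.

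Third, a reader might infer that laboratory data are analysed only as mean changes. They are not: quartiles, extremes, flags and listings are planned. With one scheduled post-baseline chemistry per period, the maximum change would show whether any scheduled rise reached 26.5 µmol/L. It would not show how many did, and by-visit summaries exclude unscheduled values (SAP 6.1).

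Fourth, the table shells are a separate document and may contain threshold tables. The finding is therefore limited to the SAP text.

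**Conclusion.** The point holds as a gap in SAP 9.4, not as a contradiction: Protocol 9.7.2 and SAP 9.4 agree with each other. The SAP text specifies no count by arm, from laboratory values, of the Appendix 6 creatinine criteria or the 6.12.8.3 enzyme multiples, and three-category shifts cannot grade them. For the liver this follows from the documents alone. For creatinine the mechanism is certain, but its size rests on assumed reference limits, baseline distribution and rise size: about 18% to 98% of stage 1 rises hidden for a mean excess of up to 0.2 mg/dL.

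A reader might infer that most stage 1 rises would be hidden. The documents do not settle this: more than half are hidden in 78% of scenarios for a rise exactly at the threshold, but in only 27% when rises exceed it by 0.2 mg/dL on average. Nor do they show how many subjects with reduced eGFR start above the creatinine range. No primary or secondary efficacy conclusion is affected. This is an inexpensive improvement to the safety analysis.

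**What to change.** Add to SAP 9.4, by treatment for 603A and the 603B withdrawal period and for the integrated set, using all scheduled and unscheduled values:

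- (a) Number and percentage of subjects whose highest post-baseline creatinine meets the Appendix 6 stage 1, 2 or 3 creatinine criteria, overall and by the eGFR ≥ 60 stratum. State how multiples between the printed bands (1.9 to 2.0, 2.9 to 3.0) are assigned.
- (b) Number and percentage with ALT or AST above 3 times ULN, above 8 times ULN, and above 3 times ULN with total bilirubin above 2 times ULN. Note that the INR and symptom criteria remain captured through adverse events; INR is not in the scheduled laboratory list.

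Add eGFR to the analysed parameters. For the 603B withdrawal period, also show creatinine against the last value before first bexagliflozin; the integrated summaries already use that baseline. Either define the grade behind the maximum-severity tables or point that sentence to these two tables.

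The cost is SAP wording and two descriptive tables from data already collected; no clinical rule changes. The downside is that table (a) will include transient, unconfirmed creatinine rises and should be labelled accordingly.

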9.5. VITAL SIGNS

Vital signs will be measured at the screening visit (Week -12), on Day -1, Day 1, cumulative week 6, 12, 12 + 1 Day, 18, 24, 24 + 1 Day, 36 and 36 + 1 Day. Measurements of vital signs will include measurement of supine and standing blood pressure (BP) measurements, and heart rate. Heart-rate in seated position will also be summarized. Orthostatic systolic and diastolic BP will be calculated as supine measurement - standing measurement. Summary tables will be provided by treatment group and visit for study 603A and 603B. An overall summary based on integrated data will be presented at 6, 12, 18, 24, and 36 weeks of bexagliflozin treatment.

Vital sign assessment on the clinical visit day is scheduled to be before the dosing of study medication. Study level baseline will be defined as the last non-missing measurement on or prior to the first dose of double-blind study medication. For integrated summary by weeks from first exposure of bexagliflozin, baseline is defined as the last non-missing measurement on or prior to the first exposure to bexagliflozin.

For BP, pulse rate, and respiration rate, observed values and change from baseline will be summarized using descriptive statistics (n, mean and median, standard deviation, Q1, and Q3, minimum and maximum) at each scheduled visit and the end of the study visit. For BP, supine, standing, and orthostatic BP will be summarized for safety analysis set.

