BP will be assessed first in the seated position. After seated BP measurement has been completed, supine and standing BP will be measured to evaluate orthostatic vital signs. Supine and standing blood pressure measures will not be used to determine eligibility for the study. The subject will lie flat for 5 min and have heart rate and supine blood pressure measured using the same equipment and arm as described for seated BP. Once the supine BP measurement is complete, the subject will stand. Standing BP and heart rate will be measured after 2 min of standing. For standing BP measurements, the arm should be supported and extended such that the cuff is at heart level. The procedure for vital sign measurement is shown in Figure 2.

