#### 6.12.8 Adverse Events of Special Interest (AEOI)

AEOI include the following categories: genital mycotic infections, urinary tract infections including urosepsis and pyelonephritis, diuretic effects including hypovolemia, hypotension episodes, hepatotoxicity, hypoglycemia, falls and fractures, malignancies, hypersensitivity reactions, acid-base disorders including DKA, renal failure events, and major adverse cardiovascular events. AEOI should be monitored carefully and documented in the CRFs.

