### **9.7.2 Laboratory Evaluations and Other Safety Assessments**

Clinical laboratory tests (see [Section 6](#) for a complete list), vital signs, and 12-lead ECG assessments will be descriptively summarized for actual values and changes from baseline (Day 1 for study 603A, and week 12 for study 603B), by treatment group and for each visit.

Laboratory data will be classified as low, normal or high relative to the parameter's reference range. Laboratory abnormalities for each treatment will also be summarized by study with shift tables for selected parameters.

In addition, summaries based on assessments from both studies (603A and 603B) will also be presented. The changes from the last assessment prior to first dose of bexagliflozin to after bexagliflozin treatment of 12 weeks, 24 weeks, and 36 weeks will be provided.

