9.3.3. AEs of Special Interest

AEs of special interest include, but are not limited to, diuretic effects, urinary tract infections (UTI), genital mycotic infections (GMI), hypoglycemia, hepatotoxicity, major adverse cardiovascular events (MACE), diabetic ketoacidosis (DKA), hypotension episodes, malignancies, fractures, renal failure events, hypersensitivity reactions, rash, pyelonephritis or urosepsis, and events may be associated with SGLT2 inhibition, including amputations, , and Fournier’s gangrene. These AEs of special interest, except for MACE, will be prospectively identified based on the MedDRA PTs in the AEs log by a medical expert prior to the data base lock and unblinding of the individual subject treatment assignment. The list of AEs of special interest will be confirmed in a peer review process. MACE and hypoglycemia events by severity will be summarized separately. All AEs of special interest will be presented for 603A, 603B run-in, 603B post-randomization, and all periods combined in the same format as in Section 9.3.2.

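### SAP 9.5 sets no criterion for an orthostatic fall and plans no count of subjects with a large measured fall, so such a fall is counted by arm only if it is reported as an AE

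*SAP*

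**What the plan says.** Protocol 6.7 has sites measure seated BP first and then supine and standing BP. The stated purpose is that "supine and standing BP will be measured to evaluate orthostatic vital signs". The schedule of events places vital signs at all eleven visits.

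SAP 9.5 turns these readings into one derived variable: "Orthostatic systolic and diastolic BP will be calculated as supine measurement - standing measurement". A positive value is therefore a fall on standing. For BP, the SAP says that "observed values and change from baseline will be summarized using descriptive statistics (n, mean and median, standard deviation, Q1, and Q3, minimum and maximum"). This applies to every planned visit and to the final one. The SAP adds: "For BP, supine, standing, and orthostatic BP will be summarized for safety analysis set". Protocol 9.7.2 plans nothing further. Its sentence covering laboratory tests, vital signs and ECG ends "12-lead ECG assessments will be descriptively summarized for actual values and changes from baseline".

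Hypotension is also handled as an adverse event. Protocol 6.12.8 includes "diuretic effects including hypovolemia, hypotension episodes, hepatotoxicity, hypoglycemia, falls and fractures" among the AEs of special interest, and SAP 9.3.3 keeps diuretic effects and hypotension episodes on its list. Apart from MACE, these events "will be prospectively identified based on the MedDRA PTs in the AEs log by a medical expert". SAP 9.3.3.1 reports them as number and percentage of subjects by treatment group and as a rate per 100 patient-years. SAP 9.3.2 tabulates all treatment-emergent AEs by preferred term.

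**The concern.** A large fall on standing happens to individual subjects and sits in the tail of the distribution. The clinical reader asks how many subjects on each arm had one. Means, medians and quartiles describe the middle of the distribution, and the maximum describes a single subject. None of them gives that number.

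The AE tables give a number, but only of events that an investigator chose to report. If a modest excess of large measured falls on bexagliflozin is not written up as AEs, the report could show nearly equal orthostatic means and few hypotension AEs, although the readings that would show the excess were taken in both arms at every visit.

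**Working it through.** **1. Is a count planned anywhere?** The documents state no orthostatic cut-off, rate or SD, so there is no figure of the plan's own to reproduce. Set side by side:

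| Item | Threshold or category planned? | Where |
|---|---|---|
| Supine minus standing BP | None; continuous statistics only | SAP 9.5, Protocol 9.7.2 |
| Laboratory values | Yes: "Laboratory data will be classified as low, normal, or high relative to the parameter's reference range", with shift tables for selected parameters | SAP 9.4 |
| Asymptomatic hypoglycemia | Yes, from the glucose value alone | Protocol 6.12.8.4, SAP 9.3.3.2 |
| BP as efficacy | Yes, for example a fall of 10 mm Hg or more in mean ambulatory SBP | SAP 4.1.2 |
| Hypotension as a harm | Count of reported AE terms | SAP 9.3.2, 9.3.3 |

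SAP 6.1 mentions shift tables in general, but only SAP 9.4 specifies any, and those are for laboratory data. SAP 12 adds nothing on this point. The protocol makes a clinically significant laboratory change (6.12.2) or ECG change (6.8) an AE. It has no matching rule for a measured fall on standing.

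**2. How far can a small cluster move the planned statistics?** The 340 per arm is the planned 680 divided by 2. The SD of the orthostatic difference, the size of the falls and the 20 mm Hg cut-off are assumptions.

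*Ten extra subjects on one arm, each with an additional 20 mm Hg fall.*
- Shift in the arm mean = 20 × 10 / 340 = 0.59 mm Hg.
- SE of the difference in means = SD × √(2/340), which is 0.61, 0.77 and 0.92 mm Hg for SD 8, 10 and 12.
- Shift divided by SE = 0.96, 0.77 and 0.64. It stays below one standard error throughout.

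*Mixture model.* In the reference arm, falls are normal with mean 0 and SD 8. In the other arm a fraction f is instead centred on 25 mm Hg with SD 8. The mean shift is 25f. Its SE is √((8² + s²)/340), where s is the SD of the mixed arm (8.73, 9.68, 10.49).

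| f | Mean shift (in SE) | Median shift | Upper quartile (reference 5.4) | Expected subjects above 20 mm Hg (reference 2.1 of 340) |
|---|---|---|---|---|
| 2% | 0.50 (0.8) | 0.2 | 5.8 | 7.1 |
| 5% | 1.25 (1.8) | 0.5 | 6.4 | 14.5 |
| 8% | 2.00 (2.8) | 0.9 | 7.1 | 21.9 |

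At 2% the count more than triples (7.1 / 2.1 = 3.4) while the mean moves by less than one SE and the median by 0.2 mm Hg. By 8% the mean would show the difference too. The gap therefore concerns small clusters. At every f, the planned table still does not say how many subjects were affected.

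**The case against.** The strongest answer is that hypotension is already counted. It is an AE of special interest with its own number, percentage and rate, and orthostatic hypotension reported as an AE appears by preferred term. The AE definition in Protocol 6.12.1 includes any unfavourable and unintended sign, so an investigator may report a measured fall without a special rule. Individual values also go into subject listings (SAP 6.1). This stands: a reader might infer that orthostatic hypotension goes unreported altogether, and the documents do not support that. What stays uncounted is the narrower set of measured falls that nobody reports as AEs. Listings give no comparison by arm.

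A reader might also infer that supine and standing BP were introduced to detect orthostatic hypotension. Protocol 6.7 states only that they serve to evaluate orthostatic vital signs.

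Nor can one say that the planned summaries miss every orthostatic effect. A shift of the whole distribution would be plain in them: 3 mm Hg at SD 10 is 3 / 0.77 = 3.9 SE. The corresponding tail counts, 8 and 15 of 340, differ by 2.1% with a 95% CI of about -0.7% to 4.8%. In that case the means are the more sensitive summary, so they must stay. The count is imprecise even for a cluster: if all ten extra subjects cross the cut-off, 8 against 18 of 340 gives 2.9% with a 95% CI of 0.07% to 5.8%. The count adds visibility more than power.

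The prior signal is weak. Protocol 3.2.2 cites one hypotension event at 20 mg in completed studies, and Protocol section 1 says that orthostatic hypotension was rare in a meta-analysis of the class. That limits the urgency. However, baseline SBP in that meta-analysis was around 130 mm Hg, whereas this trial enrols subjects with a seated SBP of 140 to below 180 mm Hg on up to four antihypertensives.

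Finally, the table shells are a separate document (SAP 15) and might hold a categorical table. The SAP text specifies none.

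**Conclusion.** The point holds in a limited form. SAP 9.5 pre-specifies neither a criterion nor a subject count for a measured orthostatic fall, and the AE route covers only the falls that are reported. The text comparison alone establishes this.

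The size rests on assumed values: 340 per arm, an SD of 8 to 12 mm Hg and a 20 mm Hg fall. On those, ten extra affected subjects (2.9%) move the mean by 0.59 mm Hg, which is 0.64 to 0.96 of a standard error. The planned location statistics are weakest for clusters of about this size and become informative as the cluster grows. No primary or secondary endpoint, error rate or sample size is affected. This is a worthwhile and cheap improvement to the safety reporting of a named harm.

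**What to change.** Keep the planned summaries and add the following to SAP 9.5.

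- An analysis criterion for an orthostatic fall in SBP and DBP, chosen and sourced by the sponsor before unblinding. The documents give none; 20 mm Hg systolic or 10 mm Hg diastolic is only an example of the form. State that it is for reporting and does not govern subject management.
- The number and percentage of subjects meeting it, by treatment and visit and at any post-baseline visit, for 603A, the 603B withdrawal period and the integrated set.
- The bexagliflozin minus placebo difference with 95% CI for 603A and for the 603B withdrawal period.
- New-onset counts (criterion not met at baseline) for 603A, and in the integrated summaries against the pre-bexagliflozin baseline that SAP 9.5 already defines. Do not use the 603B baseline for this. It follows at least 12 weeks of bexagliflozin in every subject, so the restriction would remove subjects already affected by the drug.

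If the table shells already contain such a table, the SAP text should state its criterion. The cost is one paragraph and one table from data already collected. The only downside is that a criterion must be fixed in advance.
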